### 152 2.1 Participant Recruitment and Enrollment

153 Enrollment will proceed with the goal of having up to 200 participants commencing the treatment period  
154 so that at least 160 participants complete the trial (approximately 80 participants age 6-<14 years of age,  
155 and approximately 80 participants age 14+). At least 20 participants will be age 14-<18 years of age.  
156 A maximum of 200 individuals may be enrolled into screening (ie, be consented) in the study in order  
157 to achieve this goal.

158 Study participants will be recruited from ~10-15 clinical centers in the United States without regard to  
159 gender, race, or ethnicity. There is no restriction on the number of participants to be enrolled by each site  
160 toward the overall recruitment goal.

161 In addition, there will be a study-wide goal to have at least 1/3 of completers with baseline HbA1c  $\geq 7.5\%$ ;  
162 and at least 10 completers with basal insulin rate  $>3$  units/hour (for at least part of the day).

163 Enrollment will be staged, starting with the 14+ cohort. After a cumulative 10,000 hours of use are  
164 reached in the age 14+ cohort, a Trial Level Safety Review of all adverse events and device issues will be  
165 performed before opening enrollment to the 6-13 year old cohort. Participants in this review will include  
166 the Medical Monitor, Sponsor personnel, and a medical representative from Eli Lilly. The decision to  
167 proceed with enrollment of younger participants will be driven by the totality of the safety data including  
168 any relevant device or drug  
169 data.

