## 460       **3.4 Early Discontinuation of Study Device**

461 Participants who discontinue the study device prior to 13 weeks, either by choice or by investigator  
462 decision, will be asked to come for an end of study visit and then will be dropped from the study.  
463 If the visit occurs at 6 weeks or after, blood will be drawn for the central-lab HbA1c measurement and  
464 the PROs will be completed.

465

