#### Exploratory Endpoints

960

- 961 • Postprandial incremental area under the glucose curve (4 hr)
- 962 • Peak postprandial glucose
- 963 • Times in ranges-overall and postprandial (70-180 mg/dL, >180 mg/dL, >250 mg/dL, 70-140  
964 mg/dL)
- 965 • Mean glucose
- 966 • Rate of hyperglycemia events, defined as 90 or more minutes >300 mg/dL within 120 minutes
- 967 • Overall variability (CV and SD)
- 968 • HbA1c change from baseline
- 969 • CGM metrics for hypoglycemia, hyperglycemia, and variability during daytime and nighttime

970 Patient-Reported Outcomes

- 971 • TRIM-D
- 972 • Trim-DD
- 973 • ITSQ

974 **8.5 Analysis Datasets**

975 For the main analyses, adult and pediatric participants will be pooled. Secondly separate analyses will  
976 be conducted for adults (>18 years) and pediatric (<18 years) participants. Further exploratory analyses  
977 will be conducted within pediatric subgroups.

978 All participants who initiate the Treatment Period and use the study device with the study drug will be  
979 included in the safety analyses.

980 For inclusion in the analysis of CGM metrics, participants must have at least 24 hours of CGM data  
981 during the Treatment Period.

982 **8.6 Statistical Methods**

983 **8.6.1 Analysis of the Safety Event Endpoints**

984 Safety events (ie, not including CGM defined events) will be tabulated for each type of event as the  
985 number of events per participant, the number of participants with > 1 event, and the rate of events per  
986 100 person-years.

987 Since study eligibility excluded participants with 2 or more severe hypoglycemia or DKA events in the  
988 prior 6 months, an unbiased comparison of the event rate during the Treatment Period with the pre-study  
989 event rate is not possible. Therefore, the severe hypoglycemia and DKA event rates will be compared  
990 with the T1D Exchange data, which reported the frequency of 1 or more severe hypoglycemia and DKA  
991 events in the prior 3 months according to age group; this will allow for age-matching with this trial. The  
992 proportion of participants with events during the Treatment Period will be compared with the T1D  
993 Exchange frequency using Barnard's exact test. Study endpoint will be met if severe hypoglycemia and  
994 DKA event rates are not significantly higher during follow-up compared with T1D Exchange frequency.

995 **8.6.2 Analysis of CGM Endpoints**

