15 ketoacidosis (DKA) event rates will be compared with previously published data from the T1D  
16 Exchange registry, which reported the frequency of 1 or more severe hypoglycemia and DKA  
17 events in the prior 3 months according to age group (Table 1 in Section 15). The following two  
18 hypotheses will be tested:

19 Severe Hypoglycemia:

- 20 • *Null Hypothesis:* There is no difference in the proportion of study participants who  
21 experience a severe hypoglycemic event while using Lyumjev with Control-IQ  
22 technology compared with those in the T1D Exchange registry matched by age cohort.  
23 • *Alternative Hypothesis:* There is a nonzero difference in the proportion of study  
24 participants who experience a severe hypoglycemic event while using Lyumjev with  
25 Control-IQ technology compared with those in the T1D Exchange registry matched by  
26 age cohort.

27 Diabetic Ketoacidosis:

- 28 • *Null Hypothesis:* There is no difference in the proportion of study participants who  
29 experience a diabetic ketoacidosis event while using Lyumjev with Control-IQ  
30 technology compared with those in the T1D Exchange registry matched by age cohort.  
31 • *Alternative Hypothesis:* There is a nonzero difference in the proportion of study  
32 participants who experience a diabetic ketoacidosis event while using Lyumjev with  
33 Control-IQ technology compared with those in the T1D Exchange registry matched by  
34 age cohort.

35

36

37

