## 105 **6 Calculation of Endpoints**

### 106 **6.1 Safety Endpoints**

107 An event is defined as a severe hypoglycemic event if the event required assistance of another  
108 person due to altered consciousness, and required another person to actively administer  
109 carbohydrate, glucagon, or other resuscitative actions.

110 An event is classified as a DKA event if the following occur:

- 111 • Symptoms such as polyuria, polydipsia, nausea, or vomiting;
- 112 • Serum ketones >1.5 mmol/L or large/moderate urine ketones;
- 113 • Either arterial blood pH <7.24 or serum bicarbonate (or CO2) <15; and
- 114 • Treatment provided at a health care facility

115

116 For each of the endpoints listed in Section 5.1, the total number of events for each participant  
117 and the event rate per 100 person years will be calculated. Event rates will be calculated as the  
118 total number of events occurring after the start of the treatment period divided by the number of  
119 person years the participant was active in the study. The person years will be calculated as the  
120 number of days between the start of treatment period and either the 13-week visit date or drop  
121 out date divided by 365.25.

122 The proportion of participants with at least 1 or more severe hypoglycemia and DKA events will  
123 be compared with published T1D Exchange data matched by age group (<18 years and ≥18  
124 years) (Table 1). An overall proportion will also be compared with the expected proportions  
125 from the T1D Exchange population using weights derived from the age groups. Study endpoint  
126 will be met if severe hypoglycemia and DKA event rates are not significantly higher during  
127 follow-up compared with T1D Exchange frequency.

128 A sensitivity analyses will restrict to severe hypoglycemic events occurring during the treatment  
129 period which resulted in a seizure or loss of consciousness, and DKA events which resulted in  
130 inpatient hospitalization or prolongation of existing hospitalization.

131 Adverse events occurring in the treatment phase during periods where Humalog is used will be  
132 reported separately.

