$$\frac{\text{Raw Score} - \text{Lowest Possible Raw Score}}{\text{Range of Possible Raw Scores}} \times 100$$

253 If any items are unanswered the total score and subscale pertaining to that item will not be  
254 calculated.

255 **6.5.2 ITSQ**

256 Items on the ITSQ are scored on a 7-point Likert scale. The raw total score and subscale scores  
257 are computed by calculating the mean across all non-missing item scores. Scores are then  
258 transformed to a 0 to 100 scale by using the following formula:

259 
$$\frac{7 - \text{Raw Score}}{6} \times 100$$

260 At least 75% of items must be non-missing to calculate scores.

261 **7 Analyses Cohorts**

262 All participants who initiate the treatment and provide at least 24 hours of CGM data will be  
263 included in the analyses.

264 **7.1 Analysis Windows**

265 The central lab HbA1c measured at the end of the lead-in period must be collected within 21  
266 days before to 7 days after the Lyumjev training visit, and the HbA1c measured at the end of the

267 treatment period must be collected within 42 days before to 30 days after the 13-week target date  
268 (91 days after the Lyumjev training visit). HbA1c measurements collected outside the analysis  
269 windows will be treated as missing.

270 The PRO outcomes at screening must be collected prior to the Lyumjev training visit, and PRO  
271 outcomes at 13 weeks must be collected within 42 days before to 30 days after the 13-week  
272 target date (91 days after the Lyumjev training visit). PRO outcomes collected outside the  
273 analysis windows will be treated as missing.

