## 431 **13 Multiple Comparisons**

432 The key safety endpoints will not be corrected for multiple comparisons. For all other endpoints,  
433 confidence intervals and p-values reported will be adjusted using the adaptive two stage group  
434 Benjamini-Hochberg (TST GBH) method to maintain a false discovery rate of 0.05 [3]. For  
435 multiplicity adjustments outcomes will be grouped as follows:

- 436 • Secondary safety endpoints
- 437 • HbA1c, 24 hour, daytime, nighttime, and postprandial CGM outcomes (Lead-In vs.  
438 Treatment)
- 439 • 24 Hour, daytime, and nighttime CGM outcomes (Pre-Study vs. Treatment)
- 440 • CGM outcomes following meal and exercise challenges
- 441 • 24 hour, daytime, nighttime, postprandial insulin metrics
- 442 • Insulin outcomes following meal and exercise challenges
- 443 • Subgroup analyses
- 444 • Patient reported outcomes

445

446 **14 References**

- 447 1. Brouns, F., Bjorck, I., Frayn, K. N., Gibbs, A. L., Lang, V., Slama, G., & Wolever, T. M.  
448 (2005). Glycaemic index methodology. *Nutrition Research Reviews*, 18(1), 145-171.  
449 <https://doi.org/10.1079/nrr2005100>
- 450 2. Foster, N. C., Beck, R. W., Miller, K. M., Clements, M. A., Rickels, M. R., DiMeglio, L.  
451 A., Maahs, D. M., Tamborlane, W. V., Bergenstal, R., Smith, E., Olson, B. A., & Garg,  
452 S. K. (2019). State of type 1 diabetes management and outcomes from the T1D exchange  
453 in 2016–2018. *Diabetes Technology & Therapeutics*, 21(2), 66-72.  
454 <https://doi.org/10.1089/dia.2018.0384>
- 455 3. Benjamini YB, Yekutieli D: The control of the false discovery rate in multiple testing  
456 under dependency, 2001; *Ann Stat*, 29(4):1165-1188.

457

460 **Table 1. Frequency of Acute Complications in the 2016-2018 T1D Exchange Registry Cohort**

	6–12 years old		13–17 years old		18–25 years old		26–49 years old		≥50 years old	
	N	# ≥ 1 Event (%)	N	# ≥ 1 Event (%)	N	# ≥ 1 Event (%)	N	# ≥ 1 Event (%)	N	# ≥ 1 Event (%)
Frequency of ≥1 Severe Hypoglycemia Event in Prior 3 Months a										
Overall	1313	62 (5%)	3183	155 (5%)	2445	138 (6%)	2143	157 (7%)	1976	189 (10%)
Insulin Delivery Method										
Pump	973	39 (4%)	2134	67 (3%)	1585	78 (5%)	1442	85 (6%)	1243	114 (9%)
Injections	317	22 (7%)	967	83 (9%)	817	58 (7%)	656	71 (11%)	706	74 (11%)
CGM Status										
CGM user	414	14 (3%)	584	15 (3%)	424	17 (4%)	684	36 (5%)	577	39 (7%)
CGM non-user	899	48 (5%)	2599	140 (5%)	2021	121 (6%)	1459	121 (8%)	1399	150 (11%)

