Most Recent HbA1c										
<7.0% (<53 mmol/mol)	96	4 (4%)	174	8 (5%)	257	11 (4%)	575	37 (6%)	498	51 (10%)
7.0-<7.5% (53-<58 mmol/mol)	148	4 (3%)	268	9 (3%)	283	10 (4%)	395	19 (5%)	372	41 (11%)
7.5-<8.0% (58-<64 mmol/mol)	214	9 (4%)	410	15 (4%)	341	14 (4%)	357	24 (7%)	375	30 (8%)
8.0-<9.0% (64-<75 mmol/mol)	420	19 (5%)	866	38 (4%)	596	36 (6%)	398	27 (7%)	397	35 (9%)
≥9.0% (≥75 mmol/mol)	380	25 (7%)	1370	79 (6%)	888	60 (7%)	265	36 (14%)	184	17 (9%)
Frequency of ≥1 Diabetic Ketoacidosis Event in Prior 3 Months b										
Overall	1313	31 (2%)	3183	113 (4%)	2445	96 (4%)	2143	43 (2%)	1976	22 (1%)
Insulin Delivery Method										
Pump	973	12 (1%)	2134	49 (2%)	1585	44 (3%)	1442	24 (2%)	1243	14 (1%)
Injections	317	17 (5%)	967	61 (6%)	817	51 (6%)	656	17 (3%)	706	8 (1%)

TL1 SAP V4.0 08-22-23

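### The severe hypoglycemia and DKA test sets a crude participant proportion with unequal follow-up against a 3-month registry frequency and makes no allowance for time at risk

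*SAP*

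**What the plan says.** **Tested quantity.** SAP 6.1: "The proportion of participants with at least 1 or more severe hypoglycemia and DKA events will" be compared with the registry by age group, and overall with age weights. SAP 8.1 names Barnard's exact test with a two-sided p-value.

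**Benchmark.** SAP 3 describes the registry data as the frequency of one or more "events in the prior 3 months according to age group (Table 1 in Section 15). The following two" hypotheses are then stated. The row titles of SAP Table 1 agree: "Frequency of ≥1 Severe Hypoglycemia Event in Prior 3 Months" and "Frequency of ≥1 Diabetic Ketoacidosis Event in Prior 3 Months".

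**Denominator.** SAP 7: "All participants who initiate the treatment and provide at least 24 hours of CGM data will be" analysed. Protocol 8.5: "All participants who initiate the Treatment Period and use the study device with the study drug will be" in the safety analyses. Neither sets a minimum follow-up beyond 24 hours of CGM data.

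**Early stoppers.** Protocol 3.4: those who stop the device before 13 weeks, by choice or by investigator "decision, will be asked to come for an end of study visit and then will be dropped from the study".

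**Numbers.** Protocol 2.1: "Enrollment will proceed with the goal of having up to 200 participants commencing the treatment period", so that at least 160 complete. No dropout rate is given.

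**Completers.** The 13-week visit window in Protocol 3.2 is 91 to 98 days.

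**Person-time.** SAP 6.1 computes days from the start of treatment to the 13-week visit or dropout. They are used only for the rate per 100 person-years, which SAP 8.1 tabulates and does not test.

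**Success rule.** Protocol 8.6.1 and SAP 6.1: the endpoint is met when the event rates are not significantly above the registry's. There is no margin.

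**The concern.** A 3-month frequency is a risk over a fixed window. The trial proportion is a risk over whatever window each participant happened to supply. A participant who leaves event-free at day 14 enters the test exactly like one observed event-free for 3 months.

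Under the success rule, anything that lowers the observed proportion makes a true excess harder to declare. The sensitivity analyses planned for these two endpoints narrow the event definitions and leave exposure untouched. If dropout were substantial, the report would contain no comparison with the registry on equal time at risk, although the days needed for one are already in the dataset.

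**Working it through.** The plan gives no power, alpha or dropout figure, so there is no design calculation to reproduce. The percentages in the Overall rows of Table 1 do reproduce from their counts.

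**1. Benchmarks (SAP Table 1, Overall rows).**
- Severe hypoglycemia (SH), under 18: (62 + 155)/(1313 + 3183) = 217/4496 = 4.83%. Adults: (138 + 157 + 189)/(2445 + 2143 + 1976) = 484/6564 = 7.37%.
- DKA, under 18: 144/4496 = 3.20%. Adults: 161/6564 = 2.45%.
- Age mix, assumed from the enrolment targets: 80 aged 6-13 plus 20 aged 14-17 gives 100 under 18, leaving 60 adults.
- SH: (100 × 4.83 + 60 × 7.37)/160 = 5.78%. Range 5.46% to 5.97% for 75% to 55% under 18.
- DKA: 2.92%. Range 3.02% to 2.87% over the same mixes.

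**2. Risk over unequal follow-up.** Assume constant hazard and dropout that is uniform over 91 days and unrelated to risk.
- Risk by day d: 1 − (1 − p)^(d/91).
- Average risk of a dropout: 1 − p/(−ln(1 − p)). At p = 10% this is 1 − 0.10/0.10536 = 5.09%. At p = 6% it is 3.03%.
- A completer seen at day 98, p = 10%: 1 − 0.90^(98/91) = 10.73%.

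**3. Observed risk divided by true 91-day risk, at p = 10%.**

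| Starters | Dropouts | Completers at day 91 | Completers at day 98 |
|---|---|---|---|
| 200 | 40 (20%) | (160 × 10.00 + 40 × 5.09)/200 = 9.02%, ratio 0.90 | (160 × 10.73 + 40 × 5.09)/200 = 9.60%, ratio 0.96 |
| 200 | 20 (10%) | (180 × 10.00 + 20 × 5.09)/200 = 9.51%, ratio 0.95 | (180 × 10.73 + 20 × 5.09)/200 = 10.16%, ratio 1.02 |
| 170 | 10 (6%) | (160 × 10.00 + 10 × 5.09)/170 = 9.71%, ratio 0.97 | (160 × 10.73 + 10 × 5.09)/170 = 10.40%, ratio 1.04 |

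The ratios at the DKA risk are the same to two decimals. Timing matters too: 40 dropouts all leaving at day 14, with completers at day 91, give 0.83.

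**4. Effect on the test (N = 200, alpha 0.05 assumed).** Barnard's two-sided test is approximated by giving the registry the age-weighted proportion on its 4496 + 6564 = 11,060 participants.
- SH is flagged at 19 participants with an event (p = 0.026; 18 gives 0.054).
- DKA is flagged at 11 (p = 0.033; 10 gives 0.085).

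The probability of reaching that count is binomial, with n = 200 and the observed risk from step 3. For DKA at 20% dropout and day 91, the observed risk is (160 × 6.00 + 40 × 3.03)/200 = 5.41%.

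| True 91-day risk | Full 91-day follow-up | 20% dropout, day 91 | 20% dropout, day 98 | 10% dropout, day 91 |
|---|---|---|---|---|
| SH 10% | 0.63 | 0.44 | 0.55 | 0.54 |
| DKA 6% | 0.66 | 0.52 | 0.61 | 0.59 |

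**5. What matching does to the benchmark.** For SH with 40 uniform dropouts and completers at day 91, a dropout's average benchmark risk is 2.92%. The registry expectation becomes 160 × 0.0578 + 40 × 0.0292 = 10.4 participants with an event, against 200 × 0.0578 = 11.6 as planned.

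**The case against.** - **20% dropout is a ceiling, and hard to reach.** Protocol 2.1 also caps the number consented at 200. The 40 between 200 and 160 must therefore absorb screening and lead-in failures as well. Forty dropouts among 200 starters would require every consented person to start treatment. This stands, and the 20% rows are an upper limit, not a forecast.
- **Late completers offset the loss.** Follow-up to day 98 raises the proportion by about 7% when nobody drops out. At 10% dropout it can cancel the deficit. This stands. It also means that the error can run in either direction, which is a reason to match exposure.
- **The trial's event definitions are broader than the registry's.** Table 1 counts only SH with seizure or loss of consciousness, and DKA with overnight hospitalization. The trial counts SH needing assistance for altered consciousness, and DKA treated in any health care facility. That pushes the trial proportion up, against success.
- **Some discontinuations cost little.** A participant who stops after an event already counts as an event. Protocol 3.2 lets participants attend key visits only, as an alternative to withdrawal.
- **Barnard's test is specified in the protocol, and SAP version 4.0 is dated after follow-up was complete.** Replacing the test now would be hard to defend. This stands and limits the fix to an addition.

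A reader might infer that the plan biases the primary comparison toward success. The documents do not support that as a net statement. The dropout component favours success, but late completers and the broader definitions oppose it, and neither the number nor the timing of dropouts is given.

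**Conclusion.** The exposure mismatch is real and follows from applying the SAP as written: a proportion over unequal follow-up is tested against a 3-month frequency, and the person-time that could align them is not used in any test.

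The effect is small to moderate. The observed risk is 0.90 to 0.96 of the true 91-day risk at the 20% ceiling, and 0.95 to 1.02 at 10% dropout. At the ceiling with completers at day 91, the chance of flagging the excess falls by 0.19 for SH (0.63 to 0.44) and 0.14 for DKA (0.66 to 0.52). These figures assume constant hazard, uniform non-informative dropout, alpha 0.05, N = 200, an age mix of 100 to 60, and a two-sample approximation to Barnard's test. Early clustered dropout would make the effect larger, and few dropouts would make it negligible or reverse it. The net bias of the whole comparison is not established.

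**What to change.** In SAP 6.1 and 8.1, keep Barnard's test as the protocol specifies and add one exposure-matched comparison for SH and for DKA, using the follow-up days that SAP 6.1 already computes. Either of these would serve:

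- a Kaplan-Meier 91-day risk with confidence interval, set against the age-weighted registry frequency; or
- the observed number of participants with an event, set against the sum over participants of 1 − (1 − p_age)^(days/91), where p_age is the registry frequency for the participant's age group.

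Both handle short and long follow-up alike. Name the chosen method in the SAP, and state whether treatment-phase days on Humalog count as time at risk, since SAP 6.1 reports adverse events from those periods separately. Require the endpoint conclusion to be reported with both the planned and the matched result, and record the addition as made after follow-up was complete.

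The cost is a short SAP edit and a few lines of code, with no new data. The added analysis assumes non-informative dropout, and the scaled benchmark also assumes constant hazard. The matched comparison may be slightly less favourable to the sponsor.

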## 274 **8 Statistical Analyses**

### 275 **8.1 Key Safety Analyses**

276 The total number of events, number and proportion of participants who experienced at least one  
277 event during the treatment period and the rate of events per 100 person years will be tabulated  
278 for each outcome listed in Section 5.1. The proportion of SH and DKA events will be compared  
279 to proportions of events occurring in a similar time frame among participants enrolled in the T1D  
280 exchange. These proportions have been previously published [2].

281 Barnard's exact test will be used to test the difference in proportions. A two-sided p-value testing  
282 the null hypothesis of no difference in proportions will be reported. For unanticipated adverse  
283 device effects, adverse drug reactions, and serious adverse events, the total number, number and  
284 proportion of participants who experienced at least one event during the treatment period and the  
285 rate of events per 100 person years will be tabulated.

286 All analyses described in this section will be repeated restricting to only severe hypoglycemic  
287 events that were associated with a seizure or loss of consciousness. Summary statistics will be  
288 reported for key safety outcomes by age group (6-13, 14-17, 18-25, 26-49,  $\geq 50$ ).

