**Most Recent HbA1c**

<7.0% (<53 mmol/mol)	96	0	174	1 (1%)	257	2 (1%)	575	2 (<1%)	498	3 (1%)
7.0-<7.5% (53-<58 mmol/mol)	148	1 (1%)	268	3 (1%)	283	3 (1%)	395	2 (1%)	372	2 (1%)
7.5-<8.0% (58-<64 mmol/mol)	214	3 (1%)	410	2 (1%)	341	5 (1%)	357	2 (1%)	375	0
8.0-<9.0% (64-<75 mmol/mol)	420	5 (1%)	866	18 (2%)	596	9 (2%)	398	9 (2%)	397	8 (2%)
≥9.0% (≥75 mmol/mol)	380	20 (5%)	1370	83 (6%)	888	74 (8%)	265	25 (9%)	184	5 (3%)

461  
462

a – A severe hypoglycemic event required loss of consciousness or seizure.  
b – A diabetic ketoacidosis event diagnosed by a doctor and required an overnight hospitalization.

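### The registry pass/fail test matches on age but not device: the natural reference rate is 1.27 to 1.50 times the pump and CGM-user rates for severe hypoglycemia, and 1.50 to 2.55 times for DKA

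*SAP*

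**What the plan says.** SAP 3 frames both hypotheses as the trial using Lyumjev with Control-IQ "technology compared with those in the T1D Exchange registry matched by age cohort". SAP 6.1 says the proportions with at least one event will "be compared with published T1D Exchange data matched by age group" (under 18, and 18 or older). It adds an overall proportion compared with that expected "from the T1D Exchange population using weights derived from the age groups". The endpoint is met if the severe hypoglycemia (SH) and DKA rates are not significantly higher than the registry's. Protocol 8.6.1 has the same rule and also specifies age-matching only.

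SAP 8.1 names a two-sided Barnard's exact test. No alpha is given for it. SAP 13 says "The key safety endpoints will not be corrected for multiple comparisons" and sets a false discovery rate of 0.05 for the other endpoints only.

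Table 1 in SAP 15 prints an overall row plus rows for pump users, injection users, CGM users and CGM non-users. Its footnotes define the registry events: "A severe hypoglycemic event required loss of consciousness or seizure" and "A diabetic ketoacidosis event diagnosed by a doctor and required an overnight hospitalization".

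SAP 6.1 plans a sensitivity analysis limited to SH in the treatment "period which resulted in a seizure or loss of consciousness, and DKA events which resulted in" hospitalization. SAP 8.1 covers only half of that: "All analyses described in this section will be repeated restricting to only severe hypoglycemic" events with seizure or loss of consciousness.

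**The concern.** Protocol 2.2.1 admits only people already using Control-IQ for at least 3 months with at least 85% active closed-loop time. All are therefore pump and CGM users. The registry's overall row is mostly people without CGM, and Table 1 shows lower SH and DKA rates among pump users and among CGM users. A higher reference rate makes it easier to be not significantly higher.

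This is the only pass/fail rule in the plan. A reader of a labeling submission could take a met endpoint to mean no worse than expected for people on this kind of technology. The planned comparison does not test that, and no comparison with the device rows is planned, although the data are already in the SAP.

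**Working it through.** The plan prints no reference proportion, so there is no figure of its own to reproduce. As a source check, CGM users plus CGM non-users equal the overall row in every age band, for N, SH and DKA.

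**1. Device mix of the overall row.** CGM non-users: 8,377/11,060 = 76%. Pump users: 7,377/11,060 = 67%.

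**2. Rates by stratum, summing Table 1 bands by count.**

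| Row | SH <18 | SH ≥18 | DKA <18 | DKA ≥18 |
|---|---|---|---|---|
| Overall | 217/4,496 = 4.83% | 484/6,564 = 7.37% | 144/4,496 = 3.20% | 161/6,564 = 2.45% |
| Pump | 106/3,107 = 3.41% | 277/4,270 = 6.49% | 61/3,107 = 1.96% | 82/4,270 = 1.92% |
| CGM user | 29/998 = 2.91% | 92/1,685 = 5.46% | 13/998 = 1.30% | 15/1,685 = 0.89% |

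**3. Weighted reference.** SAP 4 plans about 80 aged 6-13, about 80 aged 14 or older, and at least 20 aged 14-17. Taking exactly 20 gives 100 under 18 and 60 adults (an assumption). Reference = (100 × rate<18 + 60 × rate≥18)/160.

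- SH: overall 5.78%, pump 4.56%, CGM 3.86%. Overall/pump = 1.27 (95% bootstrap interval 1.18-1.37); overall/CGM = 1.50 (1.26-1.82).
- DKA: overall 2.92%, pump 1.95%, CGM 1.15%. Overall/pump = 1.50 (1.33-1.72); overall/CGM = 2.55 (about 1.8 to 4.0; only 28 CGM-row participants had an event).

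**4. Sensitivity to weighting inside the pediatric stratum.** Pooling by registry counts makes 13-17-year-olds 3,183/4,496 = 71% of the under-18 reference, while the trial plans mostly younger children. Weighting the 6-12, 13-17 and adult groups 80:20:60 is approximate, because the trial's 13-year-olds fall in the registry's older band. It gives:

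- SH: 5.73%, 4.83% and 4.06%; ratios 1.19 (pump) and 1.41 (CGM; interval 1.16-1.78).
- DKA: 2.54%, 1.62% and 1.01%; ratios 1.57 and 2.52.

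**5. Effect on the pooled verdict.** Assumptions: n=160, two-sided alpha 0.05, the 100:60 references entered as counts over the row's total N, and Barnard's test with a pooled statistic. Largest count still not significantly higher:

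| | Overall row | Pump row | CGM row |
|---|---|---|---|
| SH | 15 (p=0.055; 16 gives 0.025) | 12 (0.081; 13 gives 0.035) | 11 (0.061; 12 gives 0.025) |
| DKA | 8 (0.132; 9 gives 0.046) | 6 (0.118; 7 gives 0.029) | 4 (0.144; 5 gives 0.033) |

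The overall and CGM rows therefore disagree at 12-15 SH or 5-8 DKA cases in the pooled test.

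**6. Effect by stratum.** SAP 6.1 lists the two age-group comparisons before the pooled one, and these diverge at lower counts. P-values against the overall row and then the CGM row follow; ranges reflect different implementations of the test.

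- 3 adult DKA of 60: 0.22-0.27, then 0.018-0.030.
- 4 pediatric DKA of 100: 0.66-0.71, then about 0.04.
- 7 pediatric SH of 100: 0.32-0.35, then 0.029.

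**7. Chance of meeting the rule.** Binomial, pooled test, n=160. If true DKA were twice the CGM-row rate (2.30%), P(X≤8) = 99% against the overall row and P(X≤4) = 69% against the CGM row. At three times (3.44%) the chances are 90% and 35%.

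**The case against.** **The choice is disclosed.** Protocol 8.6.1 explains why an external reference is needed and says it will be age-matched. Both documents say the sample size does not rest on statistical principles. This stands, but it explains using the registry, not using a row with a different device mix.

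**For SH, the definitions pull the other way.** The trial counts altered consciousness needing another person's help; the registry counts only seizure or loss of consciousness. A reader might infer that the SH rule as a whole is tilted toward passing. The documents do not support that: the two effects oppose each other and nothing in the plan nets them. The restricted SH analysis removes the definition mismatch and leaves the device one. For DKA the definitions also differ, with no clear direction.

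**The CGM row is not the right answer either.** A reader might infer that it is the correct benchmark and should replace the overall row. Table 1 has no joint pump-plus-CGM row and none for closed loop. The pump row describes the participants as well as the CGM row does, and gives smaller ratios.

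**Review triggers come first.** Protocol 6.6.2 prompts a root-cause analysis at 5 SH cases or 5 serious hyperglycemic/ketotic cases overall, and at 3 of either in pediatric participants. A reader might infer that the rows can disagree only once a review has been triggered. That fits the pooled test only: three adult DKA cases split the stratum verdict below the 5-case trigger. In any case, the triggers do not alter the endpoint rule.

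**Other results do not need the registry.** Event counts, rates per 100 person-years and the lead-in versus treatment CGM comparison stand by themselves. That is true, and it limits the damage. However, the within-participant comparison covers CGM metrics, not SH or DKA events.

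**Conclusion.** The concern holds as a limit on what a met endpoint can show. The comparison matches on age alone, and the reference population that its wording implies differs from the trial in device use. The overall-row reference exceeds the device-row references by 1.27 (pump) and 1.50 (CGM) times for SH, or about 1.19 and 1.41 with the alternative pediatric weights. For DKA the figures are 1.50 and 2.55, or 1.57 and 2.52. The result rests on three assumptions: that the overall row is meant (the SAP does not say so), the 100:60 age mix, and alpha 0.05 for the verdict counts. Device mix alone makes the rule easier to meet; the net direction for SH is not established. The documents do not support replacing the formal rule. Supportive comparisons should be added.

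**What to change.** 1. In SAP 6.1 and 8.1, keep the pre-specified comparison as the formal rule, and name the overall row and its alpha. Add the same age-matched comparisons against the pump-user and CGM-user rows, pooled and by stratum, with confidence intervals. Do this for the main events and for the events restricted to the registry definitions. Label them supportive and added after follow-up was complete (the SAP version history puts version 4.0 at that stage). Report them beside any statement that the endpoint was met, with the caveat that the overall row is not device-matched and no joint pump-plus-CGM row exists.
2. Add the hospitalized-DKA restricted comparison to SAP 8.1 so that it agrees with SAP 6.1.

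The cost is SAP wording and tabulation of data already held. The drawbacks are that the comparisons are late and uncorrected for multiplicity, and that the CGM-row DKA rate is imprecise (weighted 1.15%, 95% interval 0.71-1.64%). If event counts are low in every stratum, the added rows will agree with the overall row and the reading will not change.
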